A randomized controlled trial to assess the performance and safety of a novel Ostomy Ring (Osto Ring™) to improve ileostomy and colostomy management
[name], [name] [name]

Background and Significance:

Ostomy surgery refers to a surgical procedure in which part of the intestine is removed and the intestinal contents are rerouted through the abdominal wall via a stoma (<http://www.niddk.nih.gov/health-information/health-topics/digestive-diseases/ostomy-surgery-bowel/Pages/ez.aspx>). This type of surgery results in the patients utilizing an external pouch, a plastic bag affixed around the stoma on the abdominal skin to collect the waste. Depending on the reason for the surgery, stomas may be temporary or permanent.

It was estimated in 2012 that there are 1 million people in the United States and Canada living with ostomies, with an additional 100,000 new ostomies created per year in the United States. (Mitchell KA, Rawl SM, Schmidt CM, et al. Demographic, clinical, and quality of life variables related to embarrassment in veterans living with an intestinal stoma. *J Wound Ostomy Continence Nurs.* 2007;34(5):524-532).

The quality of life for patients who undergo this type of surgery is significantly affected. It is an adjustment for a patient to psychologically understand that his or her body will no longer perform a bodily function “normally”. The patient needs to learn new skills such as how to correctly apply the pouching system, adjust wear time, and learn how and when to empty the pouch and remember to check the pouch seal to detect any signs of leakage. These new skills take time to learn and one of the greatest challenges is to find the best pouching system that can provide a consistent wear time to prevent leakage, embarrassment and peristomal skin issues.

A new device has been created with the aim of improving wear time and decreasing problems with leakage. The Osto Ring™ (GoDuRn LLC, [name]) is a novel and proprietary add-on modifier to the Hollister 2 piece New Image pouching system that creates a more secure seal between the patient’s peristomal skin and the skin barrier, and therefore reduces the risk of leakage.

We hypothesize that the addition of the Osto-Ring™ will reduce leakage from the stoma appliance and may also increase the length of time needed between pouch changes. Currently, the mean ostomy pouch wear time in the United States is 5.2 days (Richbourg L, Fellows J, Arroyave WD. Ostomy pouch wear time in the United States. *J Wound Ostomy Continence Nurs.* 2008 Sep-Oct;35(5):504-8), and out-of-pocket costs can be as high as \$30 with each pouching system change which translates to a yearly cost of close to \$3000. Longer wear time would therefore translate into needing fewer ostomy bags and less money spent on ostomy supplies.

Overall Objective:

The primary objective of this pre-market study is to assess the safety and performance of the Osto Ring™ as it relates to the pouching system wear time and degree of leakage.

Protocol Version #1
Dated 4/22/19

Research Design:

Study population: 30 adult subjects who have had an ileostomy or colostomy for at least 6 months, who currently use the Hollister New Image 2 piece pouching system acting as their own controls, will use their standard 2 piece New Image Hollister pouching system without the Osto Ring™ for 28 days. On Day 29 subjects will be switched to the Osto-Ring regimen until day 56. Patients will be evaluated in person at Day 0 and approximately Days 28, 56, and 75 (within business days and scheduling convenience).

The Osto-Ring for this study is being supplied by GoDuRn, LCC, and provided to subjects free of charge.

During the standard of care visit to the health care provider, subjects will be evaluated to confirm that they meet the criteria for participating in this study.

Study Design:

Day 0-27

Visit One

- **Subject will wear their standard of care Hollister 2 piece New Image pouching system for 28 days.**
 - At the first visit they will remove their pouching system to allow the investigator to assess their skin (research staff will take photo) using the Ostomy Skin Tool Reference Guide [See appendix B]
 - They will be given and asked to fill out the Quality of Life Questionnaire [See appendix C]
 - They will be given Ostomy Evaluation Record [See appendix A] and asked to complete this at every pouching system change. (And take photos of the skin site and adhesive side of the ostomy flange.)

Day 28-55

Visit Two

- **Subjects will now wear their standard of care Hollister 2 piece New Image pouching system with the Osto-Ring for the next 28 days.**
 - At the first visit they will remove their pouching system to allow the investigator to assess their skin using the Ostomy Skin Tool Reference Guide [see appendix B] (photo taken)
 - They will be fitted for the proper Osto-Ring size and given a belt.
 - They will be given and asked to fill out the Quality of Life Questionnaire [See appendix C]
 - They will be given 2 questionnaires and asked to complete them at every pouching system change. Subject will take photograph at each stoma change
 - Ostomy Evaluation Record [See appendix A]
 - Osto Ring Evaluation Record [See appendix D]

Day 56

Visit Three

Patients will decide if they want to continue using the Osto-Ring™ with their standard of care pouching system.

- Their pouching system will be removed and will have a skin assessment by the investigator using the Ostomy Skin Tool Reference Guide, Appendix B.

Protocol Version #1

Dated 4/22/19

- They will be asked how they are doing and to report any side effects they may have experienced even if they do not think it is related to the Osto-Ring™.
- They will be asked to complete :
 - The Ostomy Quality of Life Questionnaire

If they felt that the Osto Ring was helpful, subjects will be asked to extend the wear of their devices by 1-4 days per their experience (if possible). Photographs will be taken at each stoma change of the skin and the adhesive side of the flange.

Day 75

Visit Four

At this last visit, patients can decide to have their Osto Ring removed or continue using it if they like.

All four of the clinic visits are considered research-related, along with completion of questionnaires and peristomal skin assessment.

During this study, [name] and his research team will collect information about the patients for the purposes of this research. This includes their name, telephone number, medical record number, initials, date of birth, medical, surgical and medication history, date of study entry, dates of study procedures and results of tests and procedures done as part of the study.

To calculate the study sample size, data from prior studies and expert opinion was used for power analysis since this device uses a novel approach to increase wear time. The mean wear time for ileostomy pouches in the United States is 5.01 +/- 2.25 days (Richbourg L, Fellows J, Arroyave WD. Ostomy pouch wear time in the United States. *J Wound Ostomy Continence Nurs.* 2008 Sep-Oct;35(5):504-8). An increase of wear time by 25% to 6.26 days is beneficial for patient care. We determined the effect size to be 0.56 assuming that the pool standard deviation is similar to the study cited above. Using a paired t-test with a significance level of 0.05 and power of 0.8, 27 patients are needed for this study.

All patients will be recruited from the NorthShore University HealthSystem IBD center and General Surgery Clinics. Evaluation and management for any stoma related questions, concerns or assessments may also be provided by our IBD center team. Results of the study will not be made available to the sponsor or anyone with a perceived or actual conflict of interest (eg actual/potential financial relationship) until the statistical analysis has been independently completed.

Inclusion Criteria:

Subjects interested in participating in the clinical investigation must comply with the following criteria:

1. Are at least 18 years of age and have full legal capacity
2. Have had an end or loop ileostomy or colostomy for at least 6 months.
3. Have used a Hollister 2 piece New Image pouching system for at least 8 weeks
4. Able to provide informed consent
5. Have a stoma with a diameter of 57mm or less

Protocol Version #1

Dated 4/22/19

6. Change their pouching system at least two times in seven days

Exclusion Criteria:

Subjects complying with the following criteria must be excluded from participation in the clinical investigation:

1. Unable to give informed consent.
2. Are pregnant or currently breastfeeding.
3. In the last 2 months has received or is currently receiving, chemotherapy or radiation therapy.
4. In the last month has received or is currently receiving systemic or local steroid treatment in the peristomal area.
5. Currently suffering from severe peristomal skin problems such as peristomal pyoderma, abscess.
6. Currently suffering from a peristomal hernia.
7. Known hypersensitivity toward any of the test product (Osto Ring™ is made of surgical grade stainless steel)
8. In the last 30 days has participated or is currently participating in a clinical study
9. Assessed with an ostomy skin tool score of ≥ 3

Primary Outcomes:

Performance Efficacy:

To evaluate the Osto Ring™ for pouching system wear time, and degree of leakage in subjects when using the Osto Ring™ as compared to when not using the Osto-Ring™

- Integrity of the adhesive side of the flange (photos)
- Wear Time:
 - Total time pouching system worn will be calculated by the Ostomy Evaluation Record. This is defined as the difference between the dates and times the appliance is changed. (Appendix A)
- Leakage:
 - Degree of leakage at time of pouching system changes will be measured using line item from Ostomy Evaluation Record (Appendix A)

Secondary Outcomes:

1. The condition of the peristomal skin and stoma (Appendix B)
2. The number and frequency of adverse events
3. The subjects' quality of life using the Stoma Quality of Life (QoL) questionnaire (Appendix C)
4. Subject Ease of Use (ease of application, pain level with application, comfort, convenience of use) will be assessed using Likert scale: 1 = poor, 2 = satisfactory 3= very good, 4= excellent (Appendix D)

Analysis plan:

Protocol Version #1

Dated 4/22/19

All means and frequencies will be compared between the groups with the Osto Ring™ versus the group without it and will be controlled for the order in which a subject used the Osto Ring.

- Wear Time:
 - Mean days in between pouching system changes
- Leakage:
 - Frequency of any degree of leakage at pouching system changes
 - Frequency of much leakage at time of pouching system change
- Skin condition:
 - % of patients with moderate to severe skin conditions at time of each WOC nurse or physician study visit
 - Mean % of time with moderate to severe skin conditions throughout the 4 week interval at every WOC nurse or physician study visit
- Quality of Life:
 - Mean quality of life scores
- Time per Ostomy Care Session
 - Mean minutes spent during ostomy care session
- Ease of Use
- Mean % of time ease of use reported as very good or excellent by subject , Satisfaction and Confidence
 - Mean satisfaction and confidence scores
- Device Recommendation
 - % of subjects reporting they strongly agree to recommend the device to others

We will compare the baseline characteristics of the two groups. Continuous variables will be compared with the paired *t* test, and categorical variables were compared with the Fisher exact test. Each item on the ostomy evaluation record form will be individually reported.

Safety Assessments and Termination Guidelines

WOC nurses will perform skin assessments at key times. Patients are to be told that they must mention any deviation from their baseline ostomy pouching system changing routine. Failure to do so will result in a protocol violation. Patients receiving an Ostomy Skin Tool score of ≥ 3 without a known cause will be withdrawn from the study.

Any patient suffering an allergic reaction to either product (the standards New Image Hollister appliance or Osto Ring) or suspected of having an adverse reaction of any kind as determined by the patient and/or the ostomy will be removed from the trial, return for clinical assessment as indicated and return to their standard stoma care appliance.

The data safety monitoring committee will consist of Drs [name] and [name], who will review any unanticipated adverse events and have the authority to stop the trial at any time if any safety concerns are raised.

Osto-Ring™ Risks

Side effects may include:

- allergic reaction to the ring,
- worsening of the peristomal skin condition, or
- prolonged time needed in changing the ostomy pouching device.

2-piece New Image Hollister Pouching System

The 2 piece New Image Hollister Pouching System is standard of care. Concerns regarding this system will be handled by the regular physician. However, all concerns will be addressed.

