Appendix C

Ostomy Quality of Life Questionnaire

1. I feel the need to know where the nearest toilet is

Always	Sometimes	Rarely	Not At All
(1)	(2)	(3)	(4)

2. I become anxious when the pouch is full

Always	Sometimes	Rarely	Not At All
(1)	(2)	(3)	(4)

3. I feel tired during the day

Always	Sometimes	Rarely	Not At All
(1)	(2)	(3)	(4)

4. I am afraid of meeting new people

Always	Sometimes	Rarely	Not At All
(1)	(2)	(3)	(4)

5. It is difficult to hide the fact that I wear a pouch

Always	Sometimes	Rarely	Not At All
(1)	(2)	(3)	(4)

6. My stoma makes it difficult for me to be with other people

Always	Sometimes	Rarely	Not At All
(1)	(2)	(3)	(4)

7. I sleep badly during the night

Always	Sometimes	Rarely	Not At All
(1)	(2)	(3)	(4)

8. I feel lonely even when I am with other people

16. I worry that the pouch may smell

Always	Sometimes	Rarely	Not At All
(1)	(2)	(3)	(4)

17. My stoma makes me feel sexually unattractive

Always	Sometimes	Rarely	Not At All
(1)	(2)	(3)	(4)

18. I worry about noises from the stoma

Always	Sometimes	Rarely	Not At All
(1)	(2)	(3)	(4)

19. I worry that the pouch will loosen

Always	Sometimes	Rarely	Not At All
(1)	(2)	(3)	(4)

20. My stoma pouch limits the choice of clothes that I can wear

Always	Sometimes	Rarely	Not At All
(1)	(2)	(3)	(4)

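### At Visit Two the quality-of-life form that closes the control period is listed after ring fitting; it should be completed before the ring and belt are shown.

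*Combined protocol and SAP*

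**What the plan says.** Under Research Design, the in-person visits are set out as follows: "Patients will be evaluated in person at Day 0 and approximately Days 28, 56, and 75". The change of regimen is placed just after the second visit: "On Day 29 subjects will be switched to the Osto-Ring regimen until day 56".

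Under Study Design, Visit Two falls beneath the Day 28-55 heading, which opens with "Subjects will now wear their standard of care Hollister 2 piece New Image pouching system with the Osto-Ring for the next 28 days". The items then run in this order:

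1. Skin assessment with the pouching system removed.
2. Ring fitting: "They will be fitted for the proper Osto-Ring size and given a belt".
3. The quality-of-life form: "They will be given and asked to fill out the Quality of Life Questionnaire [See appendix C".
4. The two records to be completed at each later pouch change.

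The numbers are mine; the protocol uses plain bullets. Visit One (Day 0) also includes the questionnaire. At Visit Three (Day 56) subjects are asked to complete "The Ostomy Quality of Life Questionnaire".

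Quality of life is the third secondary outcome. The Analysis plan lists mean scores for it, under the general rule "All means and frequencies will be compared between the groups with the Osto Ring™ versus the group without it". It does not say which visit supplies which condition.

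**The concern.** Each subject is their own control, so the quality-of-life result depends on a few single-visit readings. The Day 28 reading carries most weight on the control side, because it alone can reflect how the subject fared over the 28 days observed without the ring.

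The subject cannot be blind to the ring, and the questionnaire asks about matters that a sealing device is meant to improve. Item 19 of Appendix C is "I worry that the pouch will loosen", and item 16 concerns worry about smell. A subject who has just been fitted may answer such items partly with the new device in mind. What is at stake is how cleanly the without-ring value of one secondary outcome is measured. Which visit feeds which condition can be settled at analysis, but a form already completed after fitting cannot be taken again under the intended conditions.

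**Working it through.** The plan gives no effect size, standard deviation or correlation for quality of life, so it has no figure of its own to reproduce on this point. Its one design calculation, 27 patients from an effect size of 0.56, concerns wear time and plays no part here. The check is therefore a comparison of sections and a short piece of algebra.

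**Which readings exist**

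| Reading | Visit | Ring status | Covers the 28-day control period? |
|---|---|---|---|
| Day 0 | One | Without ring, before any fitting | No, precedes it |
| About Day 28 | Two | Without ring by the Day 29 switch; fitting takes place at the same visit | Yes, closes it |
| About Day 56 | Three | End of the ring period | No |

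Only the second row can stand for the control period.

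**Whether the list reads as a sequence**

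Visit One runs: skin assessment, questionnaire, take-home record. Visit Two keeps that pattern and inserts fitting between the skin assessment and the questionnaire. Fitting follows naturally while the pouching system is off for the skin assessment. A coordinator working down the list would give the form after fitting. Nothing requires that order and nothing prevents it.

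**What a shift would do**

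Assume that scores without the ring are stable at m, that the true ring effect is D, and that fitting moves the Day 28 score by s. Both D and s are unknown. Then Day 0 = m, Day 28 = m + s and Day 56 = m + D.

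- Day 56 minus Day 28 = (m + D) − (m + s) = D − s.
- Day 56 minus the mean of Day 0 and Day 28 = (m + D) − (m + s/2) = D − s/2.
- Day 56 minus Day 0 = (m + D) − m = D.

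Appendix C scores run from 1 (always) to 4 (not at all), so for these items a higher score is better. If fitting reassures the subject, s is positive and a true benefit is understated. If an unfamiliar ring and belt cause worry, s is negative and the benefit is overstated. If the form is completed before the device is seen, s from this source is zero. The documents give no value or sign for s, so no numerical size can be attached.

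**The case against.** The strongest reply is that the plan never says the form follows fitting. The bullets are unnumbered, the Day 29 switch means that no ring wear should precede the Day 28 form, and being fitted is not the same as wearing the device for a period. Day 0 also supplies a without-ring reading that fitting cannot have touched, in subjects with at least 6 months of stoma experience and at least 8 weeks on this pouching system. All of this stands, and it limits the point to a possible bias. It does not remove the point: Day 0 replaces Day 28 only if scores are stable over the control period, which is an assumption, and nothing in the text protects the reading taken to represent that period.

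A reader might go further and infer that the Day 28 score is counted with the ring, because Visit Two sits under the ring-period heading, and that the estimated effect is then halved. The documents do not support this. No sentence assigns Day 28 to the ring condition. The headings mark the visit that opens a period, as the Day 0 form under Day 0-27 shows. Day 56 has its own heading, so strict assignment by heading would not pool it with Day 28, and the halving depends on that pooling.

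A reader might also infer that the questionnaire lacks a recall period. The available text of Appendix C breaks off at item 8 and resumes at item 16, so the absence of an instruction line there shows nothing about the form itself.

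**Conclusion.** The point holds as an avoidable risk in the conduct of Visit Two. The form that closes the control period is listed after ring fitting, and if staff follow that order the last without-ring reading may be moved by expectation. This rests on two assumptions: that the list is used as a working order, and that introducing the device can influence answers about pouch security and smell. Both are plausible and neither is shown. The direction and amount of any shift are unknown, so the documents support neither a claim of demonstrated bias nor one of a particular loss of effect.

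The reach is narrow. One secondary outcome is involved. Wear time, leakage and the sample size are untouched, and the Visit Two skin assessment is already listed ahead of fitting. The absence of a rule linking visits to conditions is a lesser matter, which an analyst would probably resolve sensibly; it is worth a sentence while the text is open. The change is worth making because it costs almost nothing and must be in place before the forms are completed.

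**What to change.** In Study Design, Visit Two, move the questionnaire bullet ahead of the fitting bullet and add that the form is completed on arrival, before the ring and belt are shown or fitted.

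As a supporting clarification, add one sentence to the Analysis plan: for quality of life, Day 28 is the end-of-control (without-ring) value and Day 56 is the with-ring value.

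The cost is one reordered bullet, one added clause and one added sentence. No extra visit, form or subject is needed, and the questionnaire wording stays as it is.

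### Side effects are actively asked about only at Day 56, so adverse-event ascertainment is uneven between the control and ring periods, and the safety content of Visit Four is under-specified

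*Combined protocol and SAP*

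**What the plan says.** **Outcome and comparison.** The Overall Objective makes safety part of the primary objective. Secondary Outcomes, item 2, is "The number and frequency of adverse events". The Analysis plan gives adverse events no line of their own. They fall under its opening rule that every mean and frequency is compared between use with the ring and use without it.

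**Visits.** Research Design states: "Patients will be evaluated in person at Day 0 and approximately Days 28, 56, and 75". Study Design then itemises each visit. At Visit Three (Day 56): "They will be asked how they are doing and to report any side effects they may have experienced", whether or not the subject blames the ring. Visits One and Two list a skin assessment, the quality-of-life questionnaire and diaries, but no such question. The whole Visit Four (Day 75) entry is: "At this last visit, patients can decide to have their Osto Ring removed or continue using it if they like".

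**After Day 56.** Continuing with the ring is optional. Of those who found it helpful, the plan says "subjects will be asked to extend the wear of their devices by 1-4 days per their experience", and then "Photographs will be taken at each stoma change of the skin and the adhesive side of the flange".

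**General statement.** After the Visit Four entry, Study Design adds: "All four of the clinic visits are considered research-related, along with completion of questionnaires and peristomal skin assessment".

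**The concern.** The adverse-event comparison is within subject, control period against ring period, so it is fair only if events are looked for in the same way in both. As written, a subject finishing the ring period is asked directly about side effects, and a subject finishing the control period is not. A difference in counts could then reflect who was asked rather than what happened. Analysis cannot recover events that nobody asked about.

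The second issue is the phase after Day 56. Subjects are asked to wear the system longer, and Safety Assessments and Termination Guidelines names worsening peristomal skin as a possible side effect of the ring. Yet the visit that ends this phase itemises neither a side-effect question nor an Ostomy Skin Tool score, although other sections suggest that a skin assessment is meant.

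**Working it through.** The plan gives no figure on this point, and its sample-size calculation has no bearing on it. The check is a side-by-side reading of what is listed for each phase, followed by two small calculations.

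**Listed ascertainment by phase**

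| Source | Control period (closes at Visit Two) | Ring period (closes at Visit Three) | After Day 56 (closes at Visit Four) |
|---|---|---|---|
| Side-effect question at closing visit | No | Yes | Not listed |
| Ostomy Skin Tool (Appendix B) at closing visit | Yes | Yes | Not itemised |
| Appendix A, item 2 (skin damage), each change | Yes | Yes | No instruction given |
| Appendix D problem item and free text, each change | No | Yes | No instruction given |
| Skin photographs, each change | Yes | Yes | Yes |

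The skin item under Visit Two speaks of a first visit. Because it stands in the Visit Two list, I read it as Day 28.

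1. *General adverse events.* Two prompted sources, the Visit Three question and Appendix D, exist for the ring period and neither exists for the control period. Both imbalances run the same way.
2. *Skin harm.* The Skin Tool closes both 28-day periods and Appendix A asks about skin damage at every change in both. Ascertainment is even.
3. *After Day 56.* Photographs are the only safety-relevant item explicitly listed. The Analysis plan gives no scoring rule or analysis for skin photographs.

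**Time after the only side-effect question.** Ring use starts at Day 28, the question is at Day 56 and the last visit is at Day 75.

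- Ring days to the last visit: 75 − 28 = 47.
- Ring days after the question: 75 − 56 = 19.
- Share: 19 / 47 = 0.40.

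This applies only to a subject who keeps the ring to Day 75, on the nominal schedule.

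**Effect of uneven prompting (illustration).** Assume equal true event rates in two periods of equal length. Let *c* be the share of prompted events that would also be reported spontaneously. The apparent ring-to-control ratio is 1/*c*.

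| Assumed *c* | Apparent ratio |
|---|---|
| 1.00 | 1.0 |
| 0.75 | 1.33 |
| 0.50 | 2.0 |

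The documents give no value for *c*. The illustration covers events with no even prompt, so it does not apply to skin damage.

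**Recall window.** The Visit Three question states none. It could bring out control-period events, but four weeks or more after they occurred, and no rule assigns them to a period. Correct assignment would reduce the imbalance; counting them with the ring would increase it.

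**The case against.** The best defence is that the plan holds more safety data than the visit lists suggest. Skin worsening, one of three ring side effects that the plan names, is actively and evenly measured in the two 28-day periods. Reactions to either product lead to removal and clinical assessment as indicated, and a committee reviews unanticipated events. Nurses also assess skin at times not further specified. All of this stands, and it confines the imbalance to the general solicitation of adverse events. The reaction route does not restore balance there, because it has no scheduled prompt.

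A reader might infer that the longer-wear phase yields no safety data. The documents do not support that: skin and flange photographs are listed for every change.

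A reader might also infer that Visit Four omits a skin check. That is not established. Research Design calls Day 75 an in-person evaluation, the general statement on the four visits names peristomal skin assessment, and the Analysis plan reports skin condition at each nurse or physician study visit. Visit Four is under-specified rather than clearly without a skin assessment. Still, Visits One to Three each itemise that assessment and Visit Four does not, and none of these three statements mentions side effects.

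Two further readings go too far. The ratio of 2.0 is not an estimate; it follows from an assumed capture of 50%. Nor would the imbalance hide harm in the main comparison: it would more likely make the ring look worse.

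Finally, the with-versus-without comparison of adverse events rests on a general rule, since the Analysis plan has no adverse-event line. That is true, but the rule covers all frequencies and the outcome is itself a number and frequency.

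**Conclusion.** The point holds in a limited form. Followed as written, the plan prompts for general side effects once, at the end of the ring period, and adds a ring-only problem item. The comparison for secondary outcome 2 therefore rests on uneven ascertainment and is likely to overcount events with the ring. The size is unknown; the range of 1.0 to 2.0 depends wholly on the assumed capture. Skin harm in the two 28-day periods is not affected.

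For the phase after Day 56, the conclusion is that the schedule needs reconciling: a skin assessment at Visit Four is implied elsewhere but not itemised, and no side-effect question is listed. Up to 40% of a continuing subject's ring days fall there. The change should be made, because safety is in the primary objective and the remedy is cheap.

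**What to change.** - Ask one identically worded side-effect question at Visits Two, Three and Four, each time about the period just ended, and record the period to which each event belongs.
- List the Appendix B score under Visit Four, so that the entry agrees with Research Design, the general statement on the four visits and the skin line of the Analysis plan.
- Add an adverse-event line to the Analysis plan. Base the with-versus-without comparison on the two 28-day periods, and keep Appendix D problem reports apart because they have no control counterpart.
- Report safety for Days 56-75 separately. That time adds to ring exposure only and comes from subjects who chose to continue.

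The cost is a small amendment and a few minutes at visits that already take place in person. It needs no new visit or rating scale and changes no clinical rule.

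### As written, the wear-time rule has no exception for pouching systems removed at Visits Two and Three; if those removals are logged as changes, the estimated gain shrinks modestly on average

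*Combined protocol and SAP*

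**What the plan says.** - **Primary Outcomes, Wear Time.** Wear time comes from the Ostomy Evaluation Record: "This is defined as the difference between the dates and times the appliance is changed".
- **Analysis plan, Wear Time.** The summary measure is "Mean days in between pouching system changes". Neither place mentions changes made because of a study visit.
- **Study Design, Visit Two.** Before the ring is fitted, "they will remove their pouching system to allow the investigator to assess their skin using the Ostomy Skin Tool Reference Guide".
- **Study Design, Visit Three.** "Their pouching system will be removed and will have a skin assessment by the investigator".
- **Research Design.** Visits fall on approximate days, "within business days and scheduling convenience".
- **Study Design, Visit One.** Subjects receive the Record and are "asked to complete this at every pouching system change". Appendix A likewise asks for one Record per change. It has no field for the reason for a change.
- **Related data.** The plan collects "dates of study procedures and results of tests and procedures done as part of the study" (Study Design, after Visit Four). Patients are also told that "they must mention any deviation from their baseline ostomy pouching system changing routine" (Safety Assessments and Termination Guidelines).

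No section says whether a removal in clinic counts as a change, and none excludes or censors a gap that a visit ended.

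**The concern.** Each 28-day period ends with the system coming off in clinic. Unless a change happened to be due, the last gap is shorter than the subject would have worn that system. Followed literally, the definition averages this cut gap with the complete ones.

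Both period means fall, but not equally. If the ring lengthens wear, the ring period holds fewer gaps, so its one cut gap carries more weight, and a longer gap also loses more when it is cut. The difference between periods therefore shrinks. More subjects would not help, because the cause is the design and the counting rule rather than sampling error.

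What is at stake is the size of a primary estimate. The sample-size section treats a 25% increase as beneficial, so the size of the gain matters as well as its p-value.

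**Working it through.** **1. The plan's own figure.** Effect size = (6.26 − 5.01)/2.25 = 1.25/2.25 = 0.556, stated as 0.56. A two-sided paired t test at 0.05 (two-sided is assumed; the plan does not say) has power 0.7998 at n = 27 with 0.56. The stated 27 is reproduced to rounding.

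**2. Inputs.**
- From the documents: two 28-day periods, each closed by a removal. Inclusion criterion 6 requires at least two changes in seven days, so usual wear is at most about 7/2 = 3.5 days.
- Assumed: a true 25% gain; each period starts with a fresh system; a clinic removal is logged as a change; visits are unrelated to the change cycle; gaps follow a gamma distribution with within-subject coefficient of variation (CV) 0.15, 0.30 or 0.45.

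**3. Formula.** With N completed gaps before the visit, the literal subject mean is 28/(N + 1). Since N + 1 averages roughly 28/m + 0.5 for true mean wear m, the literal mean is about 28/(28/m + 0.5).
- m = 3.5: 28/8.5 = 3.294.
- m = 4.375 (25% longer): 28/6.9 = 4.058.
- Literal gain 4.058 − 3.294 = 0.764, against a true 0.875, a loss of 12.7%.

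**4. Simulation** (200,000 subjects per cell; the three values are for CV 0.15/0.30/0.45).

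| Baseline (days) | True gain | Literal gain | Share lost |
|---|---|---|---|
| 2.0 | 0.500 | 0.463/0.467/0.469 | 6–7% |
| 2.5 | 0.625 | 0.570/0.572/0.578 | 8–9% |
| 3.0 | 0.750 | 0.670/0.675/0.679 | 9–11% |
| 3.5 | 0.875 | 0.759/0.773/0.790 | 10–13% |

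For baselines spread evenly over 2–3.5 days the mean is 2.75 and the true gain 0.25 × 2.75 = 0.6875 day. About 8–10% is lost, or 0.06–0.07 day. Against a standard error of 2.25/√27 = 0.433 day (taking 2.25 as the SD of paired differences), that is 0.06/0.433 to 0.07/0.433, about 0.14–0.16 of a standard error.

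**5. Visits that coincide with due changes.** If half do, the literal gain at 3.5 days is 0.816/0.822/0.835, a loss of 5–7%.

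**6. Perfectly regular gaps.** The result then depends on how 28 divides.
- 2.5 to 3.125 days: 28/12 = 2.333 and 28/9 = 3.111. The gain reads 0.778 against 0.625, an overstatement.
- 3.5 to 4.375 days: 28/8 = 3.5 and 28/7 = 4.0. The gain reads 0.50 against 0.875, a 43% loss.
- Regular subjects mixed over 2–3.5 days lose about 8% on average.

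**7. No true effect.** With cut gaps included, the simulated false-positive rate at n = 27 is 4.8–5.0%.

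**8. Does excluding cut gaps work?** Subject means of completed gaps give 0.872–0.880 at 3.5 days, against 0.875. Power at n = 27 with cut gaps included versus dropped, at a 3.5-day baseline:
- between-subject SD 1.575: 0.775/0.709/0.620 versus 0.769/0.694/0.588;
- between-subject SD 2.25: 0.519/0.501/0.440 versus 0.496/0.471/0.412.

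**The case against.** The strongest reply is that the premise is inferred. The outcome is defined by changes, while the visit text speaks of removal, and subjects complete the Record themselves. Visits are only approximately timed, so they could be booked on due-change days. Staff are present at the removal, visit dates are collected, and deviations from routine must be reported. The bias is small and conservative, and removing it does not improve the test.

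Much of this stands. Logging a clinic removal as a change, and visit timing unrelated to the cycle, are assumptions. Coincidence with due changes reduces the loss. The percentages also depend on assumed gap variability: a wider set of assumptions, adding between-subject spread, gave 10–17% at 3.5 days. What the reply does not supply is a rule. Matching dates finds visit-day changes but does not separate a due change from a forced one, and no analysis step uses those dates.

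A reader might infer more than the documents support:
- **A loss of 14–19%.** This follows from the sample-size means (5.01 to 6.26 days), but criterion 6 excludes a usual wear of 5.01 days.
- **A large loss of power.** Putting the shrunken gain of 1.03 days over an unchanged SD of 2.25 gives about 63% power at n = 27. That overstates the harm, because counting cut gaps also narrows the spread.
- **A spurious benefit.** With no true effect, both periods are cut alike.
- **Inflation from Days 56–75.** Only subjects who found the ring helpful are asked to extend wear then, so pooling those days would push the gain upward. The plan does not say that they are pooled, and it hands out the Record only at Visits One and Two. No figure can be put on this from the documents.

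**Conclusion.** The point holds as a modest bias in the estimate of a primary outcome, cheap to remove. If clinic removals are logged as changes and visits do not fall on due changes, the literal definition understates a true gain on average. Under the stated assumptions the understatement is about 8–10% (0.06–0.07 day) for baselines spread over 2–3.5 days, a range assumed from criterion 6. It is 10–13% at the 3.5-day ceiling, and roughly half as much if half the visits coincide with due changes. With near-regular gaps the error at a given baseline can go either way. The concern is the size of the estimate; it does not invalidate the test.

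**What to change.** In the Analysis plan:

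1. Exclude visit-ended gaps that were not due changes from each subject's own period mean, then apply the paired t test to the subject means. Alternatively, treat those gaps as right-censored in a time-to-change model clustered by subject.
2. Identify them by matching change dates to visit dates, and add a reason-for-change box to Appendix A with study visit as an option.
3. Limit the primary comparison to the two periods bounded by the actual Visit Two and Visit Three dates, and report Days 56–75 separately as descriptive. Assign each gap to the system actually worn, since Research Design places the switch on Day 29 while Study Design heads the ring period as Days 28–55.

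Two shortcuts should be avoided. Dividing total time by the number of the subject's own changes overstated the gain by 10–40% in simulation. Pooling completed gaps across subjects still lost 0.4–5.6% at a 3.5-day baseline.

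The cost is a few sentences and one tick-box. About one gap per subject per period is dropped, of roughly 7 to 9 at a 3.5-day baseline, for about 1–3 points of simulated power. Censoring costs about the same and adds a model assumption.
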